Appendix E - Hepatic Monitoring Tests for Treatment Emergent Abnormality

Selected tests may be obtained in the event of a treatment-emergent hepatic abnormality and may be required in follow-up with patients in consultation with the Lilly CRP.

Hepatic Monitoring Tests

Hepatic Hematology^a	Haptoglobin^a
Hemoglobin (HGB)	
Hematocrit (HCT)	
Erythrocytes (RBC)	
Leukocytes (WBC)	
Neutrophils ^b	
Lymphocytes	Hepatic Coagulation^a
Monocytes	Prothrombin time (PT)
Eosinophils	Prothrombin time, INR
Basophils	
Platelets (PLT)	
Hepatic Chemistry^a	Hepatic Serologies^{a,c}
Total bilirubin	Hepatitis A antibody, total
Direct bilirubin	Hepatitis A antibody, IgM
Alkaline phosphatase	Hepatitis B surface antigen
Alanine transaminase (ALT)	Hepatitis B surface antibody
Aspartate aminotransferase (AST)	Hepatitis B Core antibody
Gamma-glutamyl transferase (GGT)	Hepatitis C antibody
Creatine phosphokinase (CPK)	Hepatitis E antibody, IgG
	Hepatitis E antibody, IgM
	Recommended Autoimmune Serology
	Anti-nuclear antibody ^a
	Anti-smooth muscle antibody ^a
	Anti-actin antibody ^a

Abbreviations: CRF = case report form; IgG = immunoglobulin G; IgM = immunoglobulin M;

INR = international normalized ratio; RBC = red blood cells; WBC = white blood cells.

^a Assayed by laboratory.

^b Neutrophils reported by automated differential hematology instruments include both segmented and band forms. Whenever a manual differential is needed to report the neutrophils, the segmented and band forms should be added together and recorded on the CRF, unless the CRF specifically provides an entry field for bands.

^c Confirmation dependent on regulatory requirements and/or testing availability.

### 3. Revision History

Statistical analysis plan Version 1 was approved prior to the first interim analysis. The first interim analysis was conducted based on data cut-off date: 18 March, 2019.

Statistical analysis plan Version 2 was approved prior to the first interim analysis. The overall changes and rationale for the changes incorporated in Version 2 are as follows:

- Updated to include providing descriptive statistics for the efficacy data at the first interim analysis without performing any formal statistical test.
- Updated the primary analysis for the primary endpoint objective response rate (ORR) to be based on response assessed per Response Evaluation Criteria in Solid Tumors (RECIST) v1.1 without confirmation. Analysis based on confirmed response is added as additional sensitivity analysis for ORR.

Statistical analysis plan Version 3 was approved prior to the primary endpoint ORR data lock. The overall changes and rationale for changes incorporated in Version 3 are as follows:

- Updated to include a sensitivity analysis of ORR and progression-free survival (PFS) based on independent review of scan images.
- Clarified that QTc will be calculated based on Fridericia formula.

## 4. Study Objectives

### 4.1. Primary Objective

The primary objective of Study J1L-AM-JZGC (JZGC) is to compare AM0010 plus pembrolizumab versus pembrolizumab alone with respect to ORR based on RECIST v1.1 for patients with treatment-naïve, Stage IV/metastatic non-small cell lung cancer (NSCLC) whose tumors are not known to have epidermal growth factor receptor (EGFR) mutations or anaplastic lymphoma kinase (ALK) rearrangements, but have high expression ( $\geq 50\%$ ) programmed death-ligand 1 (PD-L1) as determined with a Food and Drug Administration (FDA)-approved assay. AM0010 is also known as pegilodocakin and the internal Lilly identifier is LY3500518 and hereafter is referred to only as AM0010.

### 4.2. Secondary Objectives

The secondary objectives of the study are to compare AM0010 plus pembrolizumab versus pembrolizumab alone with respect to each of the following:

- progression-free survival (PFS)
- overall survival (OS)
- disease control rate (DCR)
- duration of response (DOR)
- safety and tolerability profile

### 4.3. Exploratory Objectives

- To characterize AM0010 pharmacokinetics (PK) in combination with pembrolizumab
- To further evaluate the biomarkers including immune activation markers that may correlate with efficacy outcome measures. These may include, but are not limited to:
  - Food and Drug Administration-approved PD-L1 diagnostic assay
  - immune cell infiltration
  - tumor mutational burden test
  - other assay, assessment, and test on residual tissue
  - to be conducted as part of exploratory analyses

## 5. Study Design

[figure not shown]
### 5.1. Summary of Study Design

This is an open-label, randomized, multicenter, Phase 2 trial in 100 adult male and female patients with treatment-naïve, Stage IV/metastatic NSCLC whose tumors are not known to have EGFR mutations or ALK rearrangements, but have high expression ( $\geq 50\%$ ) PD-L1 as determined with an FDA-approved assay.

Patients will be stratified according to tumor histology (squamous vs non-squamous).

Patients will be randomized in a 1:1 ratio into 1 of 2 treatment arms (Figure 5.1) as follows:

- Arm 1: Patients will receive AM0010 and pembrolizumab
- Arm 2: Patients will receive pembrolizumab alone

Abbreviations: NSCLC = non-small cell lung cancer; PD-L1 = programmed death-ligand 1; QD = once daily.

Figure 5.1. Trial design.

### 5.2. Determination of Sample Size

With 100 patients, this study has more than 80% power to detect a 25% improvement (ie, 45% versus 70%) in the ORR between AM0010 in combination with pembrolizumab and pembrolizumab alone at a 1-sided 5% type I error rate.

## 6. A Priori Statistical Methods

### 6.1. General Considerations

#### 6.1.1. Population

**Enrolled Population:** all patients who signed the informed consent form and were registered into the interactive web response system (IWRS).

**Intent-to-Treat (ITT) population:** all randomized patients per the IWRS.

Unless otherwise noted, all disposition analyses will be performed on the ITT population, all patient characteristic and efficacy analyses will be performed on the ITT population and all safety and exposure analyses will be performed on the Safety population.

All analyses will be performed by treatment arm. Unless otherwise noted, all analyses on the ITT population will be performed by assigned treatment arm and all analyses on the safety population will be performed by actual treatment received.

**Per-Protocol Population:** all patients who are in the safety population and have no important protocol deviations.

The important protocol deviations which will result in exclusion from the Per-Protocol population are listed below. This is not an exhausted list and may be amended over the course of the trial. The final list will be provided as an appendix to this SAP before performing the primary analysis of this study (i.e. approximately 6 months after last patient randomized).

- patients with disease histology other than NSCLC
- patients with European Cooperative Oncology Group (ECOG) >1 at baseline
- patients who received prior regimen in metastatic setting
- patients who do not have measurable disease at baseline
- patients receiving the incorrect randomized treatment assignment (any amount of duration)

**Response Evaluable Population:** all patients who are randomized and received any amount of study medication, have baseline adequate tumor assessment, and at least 1 post-baseline adequate tumor assessment.

**Safety Population:** all randomized patients who received any amount of study medication, AM0010 or pembrolizumab.

**PK Population:** all patients who are treated with available serum time-concentration data from randomized patients.

**Biomarker Population:** includes all patients who are treated with available biomarker data from randomized patients.

**ADA Evaluable population:** all patients who are treated (in safety population), have baseline ADA (anti-drug antibody) result, and at least one post-baseline ADA result.

### **6.1.2. Definitions and Conventions**

Study treatment refers to AM0010 + pembrolizumab or pembrolizumab.

The date of randomization is the date the patient was randomly assigned to AM0010 + pembrolizumab arm or pembrolizumab arm using the IWRS.

The date of **first** dose is the date of the first dose of any study treatments.

The baseline value of a safety assessment is the last value observed prior to the first dose.

The study day of a safety event or assessment will be calculated as:

- The difference between the date of the event or assessment and the date of first dose plus 1 for all events or assessments occurring on or after the day of first dose. For example, if an event occurs on 08 June 2018 and the date of first dose was 06 June 2018, the study day of the event is 3.
- The difference between the date of the event or assessment and the date of first dose for all events or assessments occurring before the day of first dose. For example, if an event occurs on 05 June 2018 and the date of first dose was 06 June 2018, the study day of the event is -1.

The study day of an efficacy event or assessment will be calculated as:

- the difference between the date of the event or assessment and the date of randomization plus 1 for all events or assessments occurring on or after the date of randomization.
- the difference between the date of the event or assessment and the date of randomization for all events or assessments occurring before the date of randomization.
- 1 month = 30.4375 days
- 1 year = 365.25 days

Unless otherwise noted, summaries of continuous variables will include a mean, median, standard deviation (SD), minimum, and maximum.

Unless otherwise noted, summaries of categorical variables will include the frequency and percentage (relative to the population being analyzed) of each category.

P-values will be rounded to 4 decimal places. P-values that round to 0.0000 will be presented as '<0.0001' and p-values that round to 1.000 will be presented as '>0.9999.' Confidence intervals (CIs) will be presented as 2-sided 95% CIs unless specified differently in specific analysis.

## **6.2. Handling of Dropouts or Missing Data**

With the exception of dates, missing data will not be imputed. The method of imputation for any dates that are imputed is described in the relevant section.

### **6.3. Patient Disposition**

A detailed description of patient disposition will be provided. It will include a summary of the number and percentage of patients enrolled in the study, randomized in the study, treated in the study, reasons for discontinuation from study treatment, and reasons for discontinuation from study. If the reason for discontinuation is adverse event (AE), the associated AE term will be reported. Patients who cross over from pembrolizumab to AM0010 in combination with pembrolizumab following progressive disease will be summarized as well.

Protocol violation will be summarized by treatment arm.

### **6.4. Patient Characteristics**

#### **6.4.1. Demographics and Performance Status**

Patient demographics will be summarized. Patient demographics will include the following:

- sex
- race
- ethnicity
- age
- height
- weight
- body mass index

#### **6.4.2. Baseline Disease characteristics**

Disease characteristics will be summarized. Variable of disease characteristics will include the following:

- time from initial diagnosis to randomization (months)
- initial diagnosis
- stage at initial diagnosis
- time from metastatic disease diagnosed date to randomization (months)
- PD-L1 tumor proportion score (%)
- tumor mutational burden
- smoking status
- baseline ECOG Performance Status

#### **6.4.3. Medical History**

Medical history terms will be coded using the Medical Dictionary for Regulatory Activities (MedDRA).

A summary for medical history will be presented including the count and percent of patients with any medical history record and also by body system and Preferred Term (PT).

#### **6.4.4. Prior Therapies**

Prior anti-cancer therapy and radiotherapy will be summarized. Prior anti-cancer therapy regimen, duration of the regimen, and the best response of the regimen will be summarized.

Site and duration of prior radiotherapy will be summarized.

Duration of the anti-cancer therapy and duration of the radiotherapy will be calculated as (therapy stop date – therapy start date + 1). If only month and year of a therapy is available, the day will be imputed using the 15th.

#### **6.4.5. Subsequent Anti-Cancer Therapies**

Therapies received following study treatment discontinuation will be summarized by treatment arm.

#### **6.4.6. Concomitant Medications**

All medications will be coded to the generic preferred name according to the current World Health Organization (WHO) drug dictionary. All concomitant medications will be summarized for the ITT population using the preferred name.

Selected concomitant medication such as steroid use will be summarized separately.

### **6.5. Efficacy Analyses**

#### **6.5.1. General Considerations**

##### **6.5.1.1. Population**

Unless otherwise noted, all efficacy analyses will be performed on the ITT population.

##### **6.5.1.2. Stratification Factors**

The stratification factor for the analysis of primary and secondary analyses is histology type (squamous versus non-squamous).

The stratification factors are captured in the IWRS and on electronic case report forms (eCRFs). Unless otherwise specified, all stratified analyses will be based on the stratification factor per IWRS. A cross tabulation of the frequency of each level of the stratification factor, histology type, per IWRS, and eCRF will be produced.

#### **6.5.2. Primary Endpoint: Objective Response Rate**

##### **6.5.2.1. Definition**

The primary efficacy measure is ORR as defined by RECIST v1.1 and determined by the investigator. The image scans will be reviewed by an blinded independent central radiologic review governed by an Imaging Review Charter (IRC).

The ORR is defined as the number of patients with a complete response (CR) or partial response (PR) divided by the number of randomized patients recorded between the date of randomization and the date of objectively documented progression or the date of subsequent anti-cancer therapy, whichever occurs first. For patients without documented progression or subsequent anti-cancer therapy, all available response designations will contribute to the ORR determination. For patients who continue treatment beyond progression due to suspected pseudoprogression is described in the protocol Section 7.6.

### 6.5.2.2. Hypotheses and Analyses

The null ( $H_0$ ) and alternative ( $H_1$ ) hypotheses for testing ORR are:

$$H_0: P_{AM0010+pembrolizumab} = P_{pembrolizumab}$$

$$H_a: P_{AM0010+pembrolizumab} \neq P_{pembrolizumab}$$

The comparison of ORR will be carried out using a 2-sided Cochran-Mantel-Haenszel (CMH) test stratified by the histology type, squamous and non-squamous (based on IWRS), at a type I error rate of 10%. The associated odds ratio and 95% CI will also be calculated. Rates and their corresponding 95% exact CI will be calculated by Clooper-Pearson method for each randomized arm.

### 6.5.2.3. Sensitivity Analysis of ORR

Objective response rate Sensitivity Analysis 1 (ORR1): the same primary analysis on the primary endpoint ORR will be performed on the response evaluable population.

Objective response rate Sensitivity Analysis 2 (ORR2): If the stratification factor, squamous versus non-squamous, at the IWRS and at baseline (CRF) disagrees for at least 10% for the randomized patients, similar analysis of ORR as primary analysis will be performed using the strata determined at baseline based on CRF.

Objective response rate Sensitivity Analysis 3 (ORR3): the same primary analysis on the confirmed ORR will be performed.

Objective response rate Sensitivity Analysis 4 (ORR4): the same primary analysis on the ORR including response observed beyond pseudoprogression will be performed.

Objective response rate Sensitivity Analysis 5 (ORR5): the same primary analysis on the ORR will be performed based on the independent review of scan images.

## 6.5.3. Secondary Endpoints

### 6.5.3.1. Progression-Free Survival

#### 6.5.3.1.1. Definition

Progression-free survival is defined as the time from randomization to the date of documented progression (per scan or clinical progression as determined by the investigator) or the date of death due to any cause, whichever is earlier.

The detailed censoring rules are described in [Table JZGC.6.1](#).

**Table JZGC.6.1. Rules for Determining Date of Progression or Censor for Progression-Free Survival (PFS)**

Rule	Situation	Date of Progression or Censor	Outcome
1	No baseline tumor assessments	Date of Randomization	Censored
2	No post baseline assessments and no death	Date of Randomization	Censored
3	No documented progression and no death (with a post-baseline tumor assessment)	Date of last adequate tumor assessment	Censored
4	Patient lost to follow-up (or withdrew consent from study participation) before documented progression or death	Date of last adequate tumor assessment	Censored
5	Progression per scan	Date of documented progression. If a tumor assessment was done on multiple days, use the earliest date for that assessment	Progressed
6	Clinical progression	Date of clinical progression	Progressed
6	Death without documented progression	Date of death	Progressed
7	Documented progression or death after missing $\geq$ two consecutive post-baseline tumor assessments	Date of last adequate tumor assessment before missed assessment or date of randomization, whichever is later	Censored
8	New anti-cancer therapy started without a prior documented progression or death	Date of last adequate tumor assessment before the start of new anti-cancer therapy	Censored
9	Documented progression or death after missing $\geq$ two consecutive post-baseline tumor assessments	Date of last adequate tumor assessment before the start of new anti-cancer therapy	Censored

Note: Progression-free survival and associated outcome is determined by the earliest of the dates above, if more than one situation applies. Two consecutive post-baseline tumor assessments refers to the next 2 protocol scheduled tumor assessments. Time is measured from the last adequate tumor assessment date. The window of the tumor assessment is also considered (ie, the weeks for the scheduled tumor assessments plus the window allowed for each scan is 7 days (eg, a patient who goes more than  $(2*7*9+7) = 133$  days is considered missing 2 consecutive assessments) in the first year.

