4.1 Inclusion Criteria

Eligible patients must meet the following criteria to be enrolled in the trial:

1. Signed Written Informed Consent (ICF). Patients must have signed and dated an Institutional Review Board/Independent Ethics Committee (IRB/IEC) approved written ICF in accordance with regulatory and institutional guidelines. This must be obtained before the performance of any protocol related procedures that are not part of normal patient care.
 - a. Patients must be willing and able to comply with scheduled visits, treatment schedule, laboratory tests, and other requirements of the trial.
2. **Target Population**
 - a. Patients must have histologically or cytologically confirmed NSCLC that is stage IV / metastatic.
 - b. Patients must not have had systemic treatment for incurable disease. If patients had chemotherapy as part of curative intent radical radiotherapy or surgery they should have completed the last dose of chemotherapy 6 months prior to randomization.
 - c. Patients with tumor tissue high expression of PD-L1 as defined by Tumor Proportion Score (TPS) $\geq 50\%$ and as determined by a FDA-approved PD-L1 IHC 22C3 assay is mandatory
 - d. Patients ≥ 18 years of age.
 - e. Patients with Eastern Cooperative Oncology Group (ECOG) performance status of 0 or 1.
 - f. Patients with measurable disease by CT or MRI per RECIST v.1.1 criteria.
 - g. Patients with Radiographic Tumor Assessment performed within 30 days prior to randomization.
 - i) Target lesions may be located in a previously irradiated field if there is documented (radiographic) disease progression at that site.
 - h. Patients that have completed prior radiotherapy or radiosurgery at least 2 weeks prior to randomization.
 - i) Patients with brain metastases are eligible if they are asymptomatic, or are treated and are neurologically stable for at least 2 weeks without the use of steroids or on stable or decreasing dose of ≤ 10 mg daily prednisone (or equivalent).

- i. Patients with baseline laboratory values obtained 21 days prior to randomization meeting the following criteria:
 - i) WBCs $\geq 2000/\mu\text{L}$.
 - ii) Neutrophils $\geq 1500/\mu\text{L}$.
 - iii) Platelets $\geq 100 \times 10^3/\mu\text{L}$.
 - iv) Hemoglobin $\geq 9.0 \text{ g/dL}$.

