7.5 Tumor Assessments

- CT or MRI (if allergic to contrast media) scans will be performed every 9 weeks (± 7 days) during the study treatment and during the first year from discontinuation of the study treatment, every 12 weeks (± 7 days) during the second year, and every 16 weeks (± 7 days) thereafter to evaluate response to treatment by RECIST v.1.1.
- The same radiographic procedure (includes head, chest, abdomen, and pelvis) to define measurable lesions must be used throughout the trial for each patient.
- Patients will continue the assigned trial treatments until tumor progression (by RECIST v.1.1 criteria) by CT or MRI (if allergic to contrast media), withdrawal from the trial, or intolerance of therapy not manageable with dose modifications outlined in the protocol/package insert and/or supportive care. Note: Patients with suspected radiographic pseudoprogression, in the absence of clinical deterioration, should remain on trial treatments and be rescanned at 4 weeks or later. If progression is confirmed on follow-up scan, study treatments will be discontinued or patients on Arm 2 may be eligible for crossover. Refer to Section [7.6](#).
- Patients who discontinue trial treatments with response of CR, PR, or SD will undergo CT or MRI scan evaluations per protocol until time of PD, or death, or until study completion, or initiation of subsequent anti-cancer therapy, whichever is first.
- Patients who demonstrate clinical progression before their scans are due will have an unscheduled scan conducted to document disease status by RECIST v.1.1.
- The first scheduled tumor response assessment will be performed at 9 weeks (± 7 days), and responders (CR or PR per RECIST v1.1) will have a confirmatory scan at ≥ 4 weeks after response has been established using the same technique as baseline scans.
- All CT/MRI scans for all patients randomized on the trial will be collected prospectively and submitted to a central imaging vendor for archiving. These scans may be independently reviewed at a later time at the request of Lilly.

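### The SAP's 133-day cutoff does not match its own definition of two missed scans, so some PFS events after only one missed scan are censored

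*SAP*

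**What the plan says.** SAP Table JZGC.6.1, Rule 7, censors a progression or death that comes after two or more consecutive post-baseline scans were missed. The table note gives the meaning: "Two consecutive post-baseline tumor assessments refers to the next 2 protocol scheduled tumor assessments". It then turns this into days. A patient with a gap of more than 2 × 7 × 9 + 7 = 133 "days is considered missing 2 consecutive assessments", an example that the note ties to the first year. On where the gap starts it says: "Time is measured from the last adequate tumor assessment date". It makes no exception for the baseline scan.

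The Rule 7 censoring date is "Date of last adequate tumor assessment before missed assessment or date of randomization, whichever is later". On precedence the note says: "Progression-free survival and associated outcome is determined by the earliest of the dates above, if more than one situation applies". Censoring at an earlier date therefore overrides the later event.

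The protocol sets the schedule that the rule has to match. Section 4.1 requires "Patients with Radiographic Tumor Assessment performed within 30 days prior to randomization". Section 7.5 states: "The first scheduled tumor response assessment will be performed at 9 weeks", with ±7 days on every scan. The 9-week interval applies "during the study treatment and during the first year from discontinuation of the study treatment", then becomes 12 and later 16 weeks.

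Protocol 10.2.2 counts death without prior progression as an event. It has no missed-scan exception of its own and leaves further censoring rules to the SAP.

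**The concern.** The note defines the rule by scheduled visits and applies it by a day count, and the two disagree. The day count has one 7-day allowance where the protocol gives one to each scan. Read literally, its clock can also start before randomization. In both cases a patient who missed one scan can be classed as having missed two.

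The event is then lost, and in the first interval the patient contributes no follow-up time at all. PFS is the key endpoint of the follow-up analysis in SAP Table JZGC.6.3, and duration of response uses the PFS censoring time for patients who do not progress (SAP 6.5.3.4). None of the four PFS sensitivity analyses in SAP 6.5.5.1 lifts Rule 7, so its effect would not be seen.

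**Working it through.** **Inputs.** Days are elapsed days after randomization, and schedule weeks are taken to run from randomization because Protocol 7.5 names no anchor.

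- Interval 63 days, ±7 days on each scan (Protocol 7.5). Week 9 is day 63 (window 56 to 70); week 18 is day 126 (window 119 to 133).
- Baseline lead time B: 0 to 30 days before randomization (Protocol 4.1 and 7.3).
- Cutoff: gap above 133 days from the last adequate scan (SAP Table JZGC.6.1, note).

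**Step 1, the plan's figure.** 2 × 9 × 7 + 7 = 133. It reproduces exactly.

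**Step 2, only a baseline scan exists.** The cutoff falls on day 133 − B. For B = 30 this is day 103, which is 16 days before the week-18 window opens (119 − 103).

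- Week 9 missed, progression on a week-18 scan on day 126: the gap is 126 + B, above 133 when B is 8 or more. Rule 7 then censors at randomization.
- If B is uniform on 0 to 30 (an assumption), that is 23 of 31 lead times, or 74%. With the week-18 scan on day 119 it needs B of 15 or more (16/31 = 52%); on day 133 it needs B of 1 or more (30/31 = 97%).
- Appendix D gives a lead of up to 4 weeks before Day 1. With B uniform on 0 to 28 the on-time figure is 21/29 = 72%.
- With B = 30, a death on days 104 to 118 is also censored at randomization, although only week 9 has been missed and week 18 is not yet due.

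**Step 3, between post-baseline scans.** Let the scans on either side of one missed visit be off nominal by a and b days, each from −7 to +7. The gap is 126 + b − a.

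- At nominal timing the gap is 126 and the event counts.
- The largest in-window gap is 126 + 7 + 7 = 140.
- Gaps of 134 to 140 need b − a of 8 to 14: 7 + 6 + 5 + 4 + 3 + 2 + 1 = 28 of 15 × 15 = 225 pairs, or 12.4% if offsets are uniform (an assumption). These patients are censored at the last scan, not at randomization.

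**Step 4, how many patients.** The documents give no miss rate, so this is illustrative. Assume 100 patients, exponential PFS with median 10.3 months (the pembrolizumab figure in Protocol 1.1), the same miss rate at each scan, and every event found at the scan after the missed one.

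- Over one interval, 63/30.4375 = 2.07 months, so S = 0.5^(2.07/10.3) = 0.870. The event probability over two intervals is 1 − 0.870² = 0.243.
- Censored at randomization, 5% missed: 100 × 0.05 × 0.243 × 0.742 = 0.9. At 2% and 10% missed it is 0.4 and 1.8.
- Censored at a later scan, 5% missed: 100 × 0.05 × 0.243 × 0.124 × (S + S² + …). Four later missed visits (sum 2.86) give 0.4; ten (sum 5.03) give 0.8.
- Total at 5%: about 1.3 to 1.7 patients per 100.

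**The case against.** The best defence is that the visit-based definition governs and 133 days is only an example. Counted from randomization, 126 + 7 = 133 is exactly the close of the week-18 window, which suggests what the author had in mind. On that reading the first-interval problem disappears.

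This is a fair guess at intent, but it is not in the text. The note starts the clock at the last adequate assessment without exception. Rule 7's fallback to randomization, if later, is needed only when a pre-randomization scan can be the last adequate one. A programmer following the table would count from baseline. The defence also leaves the post-baseline mismatch untouched.

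Other parts of the defence stand and limit the point:

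- Even read literally, no event up to day 103 is affected.
- Clinical progression counts on its own date, so a patient who deteriorates before the cutoff remains an event.
- After a post-baseline scan, misclassification needs an early scan followed by a late one.
- The definition by scheduled visits can be read to carry the 12- and 16-week intervals, although no cutoff is given for them.

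**Conclusion.** The day count in the note does not implement the note's own definition, and some PFS events after one missed scan are censored as a result. The limits (day 103, a lead of 8 or more days, gaps of 134 to 140 days) follow from the documents, with schedule weeks counted from randomization. The shares (74% and 12%) assume uniform timing and apply only to patients who already have the missed-scan pattern. About 1 to 2 patients per 100 rests on an assumed 5% miss rate. This deserves correction before the PFS analysis, but PFS is secondary and the primary ORR test does not use the rule.

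A reader might infer two stronger things. One is that events are often censored back to randomization. The documents give neither a missed-scan rate nor a distribution of baseline lead times, so they do not support that. The other is that confirmatory scans in responders bias the comparison by restarting the clock. A confirmatory scan is a real assessment that narrows the time in which progression could have occurred, so restarting the clock is defensible. Suspected pseudoprogression also triggers extra scans (Protocol 7.6), so they are not confined to responders. Ignoring confirmatory scans would discard valid data and add censoring.

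**What to change.** Amend the note to SAP Table JZGC.6.1:

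- With no post-baseline scan, count from randomization and keep 2 × 63 + 7 = 133 days, the close of the week-18 window. State the schedule's anchor: if weeks run from first dose, which may be up to 3 days after randomization, the window closes up to 3 days later.
- After a post-baseline scan, use two scheduled intervals plus 14 days: 126 + 14 = 140 for 9-week scans, 168 + 14 = 182 for 12-week and 224 + 14 = 238 for 16-week scans. Where the interval changes, add the two that apply.
- Replace the first-year wording with the interval in force under Protocol 7.5: 9 weeks throughout treatment and the first year off it, then 12 and 16 weeks.
- Reconcile Rule 9, which repeats Rule 7's situation with a censoring date tied to new anti-cancer therapy.
- Report the number of events censored under Rule 7 by arm.

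The cost is SAP wording and a small programming change, with no new data. The downside is that a few retained events rest on a slightly longer scan gap. If the last scan was 7 days late, both following windows have closed after 133 − 7 = 126 days, so an event at 134 to 140 days after two true misses would now count.
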